3.8.5 Visit schedule and follow-up activities

The follow-up schedule is summarized in Table 1 below. After study randomization, participants will receive follow-up for six months. At enrollment the baby will be weighed and clinical data on mother and child will be entered in the CRF. The first visit after enrolment will be around 7 days after birth, the second at six weeks after initiation of intervention product, and the last visit at six months. During all study visits, the baby's length, weight measurements, and clinical information will be recorded. Fecal samples and fecal swabs will also be taken according to the developed SOP.

Table 1. Follow-up schedule visit for ProRIDE-trial

| Time | Event | Activity |
|----------------------------------------------------------------------|-----------------------------|-------------------------------------------------------------------------------------------------------------------------------------------------------|
| Day 0-3 after birth of the newborn | Enrolment and randomization | - Filling of CRF-1 - Giving the IP/placebo to the mother/caretaker of the baby |
| Day 7 after initiation of investigational product | Visit 1 | - Observe for the compliance - Discuss issues with care takers |
| Six weeks after initiation of investigational product | Visit 2 | -Observe if the bottle with IP/placebo is empty and return the bottle -First fecal and fecal swab sample will be taken -Filling of CRF-2 |
| Six months (25-27 weeks) after initiation of investigational product | Visit 3 | -Second fecal and fecal swab will be taken - Filling of CRF-3 |

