Participants have been randomized to probiotic or placebo using fixed equal allocation ratios. An independent researcher/statistician at University of Bergen created a computer-generated randomization list, with the study identification number of patients, from 1 to 2000, allocated to probiotic or placebo. We have not planned for any restrictions to reduce the predictability of the randomization list. The probiotic and placebo are identical in taste and color, and produced in identical bottles. A pharmacist, who was not part of the study, was provided with the randomization list and labelled the identical bottles, numbered from 1 to 2000. This was performed before shipment to the study site. At the time of inclusion of infants in the ProRIDE study, study personnel provided the parents with consecutive, prelabelled bottles with probiotic or placebo according to the randomization list.

11. Sample size

Infant mortality rate in Tanzania was in 2018 reported at 3.8%. We do not have exact data for the Mbulu district, but we assume a similar rate of approximately 4%. Serious infections leading to hospitalization are probably equally common, but hospitalization rates may depend on available access. In the Panigrahi study, a synbiotic product was given for only seven days, and it reduced the composite outcome death and/or infection from 9.0% to 5.4% during the first two months of life. In our study, the intervention will continue for around four weeks and follow-up will continue until six months of life. We consider a similar reduction in the composite outcome death and infections leading to hospitalizations from 9.0% to 5.4%, as in the Panigrahi study, to be clinically relevant (1). To find this difference with a study power of 85% at 5% significance level a sample size of minimum 924 cases in each arm; thus 1848 infants is needed. In order to allow for drop-out we aimed to include 2000 infants. With this number of infants, we will also have sufficient power to detect a minimum of 30% reduction in ESBL-E colonization rate (from around 50% to 35%) at six months of age.

We finished recruitment of 2000 participants in January 2023 and will complete 6 months follow-up for all participants in July 2023.

12. Framework

The study will test the hypothesis of superiority of probiotic over placebo in preventing death or hospitalization during the first 6 months of life. Comparison of the proportion of participants with the primary outcome will be presented.

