13. Statistical interim analysis and stopping guidance

Interim analyses have been performed after six month follow-up of 500 and 1000 infants. The major outcomes and adverse outcomes of interest; mortality, hospitalizations and blood culture confirmed sepsis have been summarized and presented to the DSMB. Only the study statistician have had access to these results. If mortality between groups (probiotic vs placebo) at 6 weeks follow-up had been significantly different at the level of $p<0.05$ by Chi square test at assessment at these two time points of the study, the study would have been stopped. This decision had in that case to be taken by the PI of the study, in consultation with co-investigators and the DSMB. Other triggers that would call for an unscheduled DSMB review were if infant mortality or morbidity rates clearly exceed expected rates in Tanzania. Severe adverse events have also been reported consecutively to the DSMB, and the DSMB have evaluated this independently of the interim analysis.

14. Timing of final analysis

Final analysis of data will be performed after all patients have completed 6 months follow-up. This analysis will be performed on anonymized data. Blinding for investigators and patients will be maintained until the study is completed.

15. Timing of outcome assessments

The primary outcomes will be assessed at 6 months. Secondary outcomes will be assessed at 6 weeks and 6 months. Additionally, adverse events have been and will be reported to the DSMB consecutively for independent evaluation until the study is completed.

Statistical principles

16. Levels of significance, P values

Analysis results for the primary outcome will be reported as odds ratio with 95% confidence interval with P-value. The standard cut-off of $p<0.05$ will be used for statistical significance levels. For secondary outcomes we will report appropriate effects measures with 95% confidence intervals without p-values.

17. Rationale for any adjustment for multiplicity, and, if so how the type 1 error is to be controlled

Type I error will be controlled at the traditional 0.05 two-sided level for the hypothesis test. We will perform a hypothesis test only for the primary outcome and we will not need to adjust for multiple tests.

18. Confidence intervals to be reported

Odds ratios and other relevant effect-measures will be estimated in appropriate regression models and will be reported with 95% confidence intervals.

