Patients will be recruited among newborns; born at Haydom Lutheran Hospital (HLH) in North East Tanzania and out-born newborns in the surrounding area. HLH is located in the Mbulu district, at the western end of the Manyara region in the North-Central Tanzania, about 300 km south-west from regional center Arusha. The HLH catchment area consists of four administrative divisions, three districts and two regions. These are the Dongobesh and Haydom divisions in Mbulu District, the Basotu Division in Hanang District (Manyara Region), and the Nduguti Division in Iramba District (Singida Region). The hospital serves a population of more than two million people from five regions. Annually, there are more around 3900 deliveries in the hospital, and in 2018 the neonatal mortality rate in Tanzania was around 21/1000 live births.

24. Withdrawal / follow-up

Participation is based on informed voluntary consent of the parents of the child. Parents may decide that their child may withdraw at any time of the study without giving reasons or justification. Upon withdrawal, no further data will be collected. However, data recorded up until the time of withdrawal will be included in the analysis.

25. Baseline patient characteristics

Baseline data on demographic characteristics are recorded as detailed in the eCRF.

Analysis

26. Outcome definitions

Primary outcome

Prevalence (%) of the composite outcome death and/or hospitalizations at six months of age.

Secondary outcomes

- Rates (%) of ESBL-E colonization at six weeks and six months of age.
- Rates (%) of hospitalizations up to six months of age.
- Rates (%) of confirmed sepsis (blood culture-confirmed) episodes up to six months of age.
- Growth monitored by length and weight up to six months of age.
- Stool microbiota composition including resistome analysis (metagenome sequencing) at six weeks and six months of age.
- Stool metabolome composition at six weeks and six months of age.
- Stool inflammatory markers at six months of age
- Genetic characteristics of ESBL-E from colonization and clinical samples (targeted screening).
- Risk factors for death, hospitalization and sepsis.
- Primary and secondary outcomes will secondarily be performed stratified for place of delivery, ie hospital, home or primary health care facility.

27. Analysis methods

Clinical and microbiological data

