In univariate analysis, comparison of proportions will be done using Pearson's chi-squared test and comparison of means will be done using t-test or non-parametric tests as appropriate. Logistic regression will be used for multivariate analysis when assessing the relative importance of risk factors for carriage of ESBL-E and other multi-resistant bacteria.

Stool microbiota, stool metabolome and stool inflammatory markers

Stool microbiota: A Poisson generalized linear model will be used to calculate trends in the relative abundance of genera and antibiotic resistance genes in the stool microbiota. Corrections based on multiple comparisons will be performed by the Benjamini-Hochberg false discovery rate (FDR). An FDR Q value $\leq .10$ will be considered significant for any analyses with multiple comparisons. A standard P value $\leq .05$ will be considered significant for all other analyses. Alpha diversity of the gut microbiota will be assessed by calculating the Shannon Diversity index (MEGAN, v5.10.6). Multiple beta diversity metrics of

samples will be performed by using non-metrical multidimensional scaling (NMDS), based on a matrix of Bray-Curtis distances and calculated by using the vegan R package. Differences between groups will be tested by using permutational multivariate analysis on beta diversity matrices.

Stool metabolites will be identified by using mass spectral (MS) databases (e.g., MzCloud, Metlin) and standards purchased for this project. For statistical and pathway analyses, we will use web-based tool MetaboAnalyst. All MS data will be submitted to and stored at the European Bioinformatics Institute repository MetaboLights. Stool inflammatory markers will be analysed with conventional statistical tools for interval data using parametric or non-parametric tests, as appropriate.

28. Missing data

Missing data for both binary and continuous variables will in the main analyses be handled as non-responses. Depending on the degree of missingness, we will perform supplementary analyses with multiple imputation of missing values to assess the possibility that the missing data may introduce bias.

29. Statistical software

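### The SAP names only an unadjusted test for proportions and leaves the primary odds-ratio model and its covariates open; a small, cheap gain from prespecified adjustment is forgone

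*SAP*

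**What the plan says.** On allocation, SAP 10 states: "We have not planned for any restrictions to reduce the predictability of the randomization list". Neither document describes blocking or stratification.

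On analysis, SAP 27 says "In univariate analysis, comparison of proportions will be done using" Pearson's chi-squared test, and assigns multivariable logistic regression to risk factors for resistant carriage. Protocol 7.0 is similar: chi-squared for proportions, and logistic regression for risk factors, there including infection episodes and mortality. SAP 16 reports the primary outcome as an odds ratio with 95% interval and P-value. SAP 18 says only that odds ratios will come from suitable regression models. Neither section lists a covariate.

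On baseline data, Protocol 3.8.5 says: "At enrollment the baby will be weighed and clinical data on mother and child will be entered in the CRF". Birth weight of at least 2.0 kg is an eligibility criterion in both documents. SAP 26 plans further analyses of the primary and secondary outcomes "stratified for place of delivery, ie hospital, home or primary health care facility", so place of delivery has to be captured.

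**The concern.** The primary outcome carries the trial's only hypothesis test (SAP 17), yet a reader cannot tell from the SAP which model produces its odds ratio, or whether that model is adjusted. Read literally, the one named test ignores two baseline variables that may predict death or admission.

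Two things follow. If those variables do predict the outcome, an unadjusted estimate is slightly less precise than it could be, and it carries whatever imbalance the unrestricted list happened to produce. And if the model is chosen once results by arm are known, the choice will look data-driven even when it is innocent.

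**Working it through.** **1. The plan's own sample size.** Inputs from SAP 11 and 17: "composite outcome death and infections leading to hospitalizations from 9.0% to 5.4"%; "To find this difference with a study power of 85% at 5% significance level a sample size of minimum 924 cases in each arm"; "Type I error will be controlled at the traditional 0.05 two-sided level for the hypothesis test". For a two-proportion test with pooled variance and no continuity correction,

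n = [z(0.975)·√(2·p̄·(1−p̄)) + z(0.85)·√(p₁(1−p₁) + p₂(1−p₂))]² / (p₁−p₂)²

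with p̄ = 0.072. This is [1.960·√0.133632 + 1.036·√0.132984]² / 0.036² = 924.2 per arm, so the stated 924 is reproduced. The sample size rests on an unadjusted comparison. Power is 85.0% with 924 per arm and 87.6% with 1000.

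**2. Size of chance imbalance with 2000 infants.** For a binary factor with prevalence p, the SD of the between-arm difference in share is √(4p(1−p)/2000).
- p = 0.3 (assumed): SD 2.0 points, 95% range ±4.0 points.
- p = 0.5 (assumed): SD 2.2 points, 95% range ±4.4 points.
- Birth weight: SD of the difference in means is √(4/2000) = 0.045 SD, 95% range ±0.09 SD.

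If the risk gap between places of delivery were 5 points (assumed), an imbalance at the edge of the 95% range (4.4 points) would move the risk difference by 0.044 × 5 = 0.22 points. That is 6% of the 3.6-point target effect. The standard error of the risk difference with 1000 per arm is √(0.132984/1000) = 1.15 points, so the 95% half-width is about 2.3 points and the shift is about a tenth of it.

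**3. Gain from adjustment.** Simulation of 2000 infants, simple 1:1 allocation, 3000 trials per scenario. The chi-squared test was compared with the arm coefficient in a logistic model containing birth weight and place. Predictor strengths are assumptions: an odds ratio per SD lower birth weight, and one for a higher-risk place holding 30% of infants.

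| Assumed odds ratios (weight, place) | Power, chi-squared | Power, adjusted | Variance of risk difference removed, with effect / under null | Odds ratio, marginal / conditional |
|---|---|---|---|---|
| 1.2, 1.3 | 88.4% | 88.4% | 0.4% / 0.5% | 0.575 / 0.573 |
| 1.5, 1.5 | 88.6% | 89.1% | 0.8% / 1.7% | 0.573 / 0.568 |
| 1.8, 2.0 | 87.4% | 88.8% | 4.2% / 3.2% | 0.573 / 0.562 |

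The power gain is 0, 0.5 and 1.4 points. With equal risks of 7.2% in both arms, the chi-squared test rejected in 4.9%, 5.0% and 4.6% of trials, so it holds its level without adjustment.

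**4. Does the choice of model matter?** In a further run of the same three scenarios, the two analyses fell on opposite sides of p = 0.05 in 1.0%, 2.1% and 2.9% of trials at 9.0% versus 5.4%. At an assumed smaller effect (9.0% versus 6.75%) they disagreed in 2.5%, 4.6% and 6.2%. The choice rarely decides the conclusion, but it can when the result is borderline.

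**The case against.** The strongest case against runs as follows.

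- **The SAP does not say the primary analysis is unadjusted.** The chi-squared sentence is generic, and SAP 18 promises regression models. This stands. A reader might infer from SAP 27 that the headline estimate will be unadjusted, but the text supports only that the model and covariates are not named.
- **Place of delivery is already covered.** SAP 26 plans a stratified analysis, which would help expose an imbalance. This stands in part: that analysis is secondary, nothing says the strata are pooled into one estimate, and birth weight has no counterpart.
- **An unadjusted analysis is valid.** This stands. A reader might infer that an unrestricted list biases the comparison or inflates type I error. It does neither: randomisation balances the arms in expectation, and the ordinary confidence interval already allows for chance imbalance.
- **Predictor strength is unknown.** This stands. Poorer access could raise deaths and lower admissions, so in this composite the net effect of place could be near zero. The gain would then sit at the bottom of the range.
- **Adjustment is not free.** The eCRF is not shown, and the documents do not say how birth weight is obtained for home births enrolled up to day 3. A missing-covariate rule is therefore needed. The conditional odds ratio also differs slightly from the marginal one. Both points are met in the fix.
- **The study statistician has seen interim results (SAP 13).** A late change could therefore itself be questioned. The risk is limited if the covariates come from the eligibility criteria and SAP 26, and the change is dated before unblinding. It grows if the model stays open.

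**Conclusion.** The point holds as a minor improvement. The only named test for proportions is unadjusted, the primary regression model and its covariates are unspecified, and two baseline variables that should be to hand are not used for the headline estimate.

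The expected gain is about 0 to 1.4 points of power, or 0% to 4% of the variance, with some protection against chance imbalance and against choosing the model after the results are known. These figures rest on assumed odds ratios of 1.2 to 1.8 per SD of birth weight and 1.3 to 2.0 for place, and on an assumed 30% share in the higher-risk place. They also assume the planned event rates.

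The documents do not support a reading that the trial is underpowered, biased or invalid on this account. The stated sample size does not change.

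**What to change.** Amend SAP 16, 18 and 27, dated before unblinding:

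1. Make the primary analysis a logistic model with arm, birth weight (continuous; enrolment weight where birth weight was not measured) and place of delivery (three levels).
2. Keep the odds ratio as the primary measure. Average the model's predicted risks over all infants under each arm, and report the resulting marginal odds ratio with its 95% interval and P-value. Give the standardised risk difference alongside. The SAP should state that the odds ratio is marginal.
3. Keep every randomised infant when a covariate is missing by a simple imputation from baseline data that ignores arm and outcome. Missing outcomes remain a matter for SAP 28.
4. Show the unadjusted chi-squared result as supportive.

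The cost is a few lines of SAP text, slightly more analysis work and the missing-covariate rule. No new data should be needed, provided the eCRF holds both variables as the documents imply.

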7.0 Statistical analysis

Comparisons of proportions will be done by Pearson's chi-squared tests. Means will be compared by t-test or non-parametric tests as appropriate. Logistic regression analysis will be performed for assessment of the relative importance of risk factors for carriage of ESBL,

ProRIDE Trial in Tanzania

multidrug-resistant bacteria, infection episodes and mortality. Analysis will be performed in Stata 13 (Stata corporation, College Station, Texas).

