19. Adherence and protocol deviations

Any deviations from the protocol will or have already been documented in a protocol deviation form and filed in the study master file. A SOP is in place describing the procedure for identifying non-compliances, escalation to the central team and assessment of whether a non-compliance /deviation may be a potential Serious Breach.

20. Analysis populations

The primary analysis will be an “intention to treat” analysis performed on all patients who were randomized. In addition, per protocol analysis will be performed for patients who reported to have adhered to the ingestion of the study product (probiotic or placebo), and on other subgroups of the study population.

Trial population

21. Screening data

Pregnant women in their last trimester, visited at home or attending the last antenatal care visit at HLH, will receive oral and written information about all aspects of the study before giving consent to let their future child participate in the study. Trained research assistants who speak the local language will be in charge of obtaining informed consent before recruitment.

22. Eligibility

Inclusion criteria

Healthy newborn infants with a birth weight (BW) equal or above 2.0 kg are eligible for inclusion. Newborn infants have to come from families who are long-term or permanent residents in the defined catchment area for this trial (30 km radius from HLH) in Tanzania. Parents have to be able and willing to complete study visit (including required study procedures) schedules over the six months proposed follow-up. This also includes that they, if possible, bring their child to the hospital in case of any intercurrent illness. Parents have to sign informed consent form (ICF) and have to agree that the child cannot participate in another clinical trial during the study period

Exclusion criteria

BW below 2.0 kg, refusal of informed consent and/or other health problems/illness including obvious congenital malformations

23. Recruitment

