Statistical analysis will be performed in R version 4.2.2 or higher (The R Foundation for Statistical Computing, Vienna, Austria). Mixed effects models analysis in R will be performed using the “lme4” or “lmerTest” packages. If imputation is considered necessary or useful, regression analysis with multiple imputation will be performed, and imputation will be done using the mice.impute.bygroup function in the “mice” and “miceadd” libraries in R.

Publication plan

30. Primary outcome

The first main paper will present the effect of probiotic administration on the primary outcomes (death and/or hospitalization) and the following secondary outcomes: carriage of ESBL-producing Enterobacteriales and the taxonomy of the gut microbiota in the two study arms. Safety of the probiotics will be described in the same paper, with focus on adverse events.

31. Secondary outcomes

Further analysis of the effect of the probiotics on prespecified secondary outcomes will be published separately.

32. Cost-efficacy and ethical issues

Given a positive effect of probiotics, cost-benefit considerations of probiotic treatment will be published focusing on the perspectives of the individual patient and society at large, including data on hospitalization, healthcare use, etc.

References

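### The growth comparison has no prespecified adjustment for baseline weight, although a baseline weight is recorded for essentially every infant

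*SAP*

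**What the plan says.** Growth is objective 2.2.5 of the protocol and a secondary outcome in Protocol 2.3.2 and SAP 26, measured by length (the protocol says height) and weight up to six months.

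- **Method for means.** SAP 27, on clinical and microbiological data, says "comparison of means will be done using t-test or non-parametric tests as appropriate". The sentence opens "In univariate analysis, comparison of proportions will be done using", so the SAP itself labels the method univariate. Protocol 7.0 has the same method without that label: "Means will be compared by t-test or non-parametric tests as appropriate". The one multivariable method for clinical data in SAP 27 is logistic regression for risk factors for carriage, which does not apply to a continuous outcome.
- **Reporting.** SAP 16: "For secondary outcomes we will report appropriate effects measures with 95% confidence intervals without p-values". SAP 18: "Odds ratios and other relevant effect-measures will be estimated in appropriate regression models", with 95% confidence intervals. Neither mentions growth or a covariate.
- **Software.** SAP 29: "Mixed effects models analysis in R will be performed using the" lme4 or lmerTest packages. No outcome, fixed effect or random effect is given.
- **Baseline weight.** SAP 22: "Healthy newborn infants with a birth weight (BW) equal or above 2.0 kg are eligible for inclusion", so birth weight must be known before randomisation. Protocol 3.8.5 adds weighing at enrolment. SAP 25 says only that baseline data are recorded.
- **Randomisation.** SAP 10: "We have not planned for any restrictions to reduce the predictability of the randomization list". No stratification factor for the randomisation is named.
- **Strata.** SAP 26 plans the secondary outcomes by place of delivery as well. That uses a baseline factor, but not baseline size.

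**The concern.** Weight at six weeks or six months can be expected to depend in part on weight at birth. A comparison that ignores baseline weight leaves that part of the variation in the error term. Because the randomisation is unrestricted, baseline weight is balanced between the arms only by chance, and any chance difference carries over in part to the unadjusted growth difference.

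Under SAP 16 the estimate and its interval are the whole result for a secondary outcome, so interval width is the relevant measure of quality. There is also a question of choice. An unadjusted difference, a gain score, a baseline-adjusted regression and a mixed model are all compatible with the present text. They can give different estimates and intervals from the same data, and the plan does not say which one will be reported.

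**Working it through.** **The plan's own figure.** The documents give no calculation for growth. The number that carries over is the minimum of 924 per arm from the sample-size section (9.0% against 5.4%, 85% power, two-sided 5%). With pooled variance and no continuity correction:

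n = [1.960 × √(2 × 0.072 × 0.928) + 1.036 × √(0.09 × 0.91 + 0.054 × 0.946)]² / 0.036² = 924.2

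This rounds up to 925, and power at 924 is 85.0%. The stated figure reproduces and is used below as the number analysed per arm.

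**Inputs for growth.** n = 924 per arm. Results are in units of the outcome SD. The correlation r between baseline and later weight is not in the documents and is **assumed** to lie between 0.2 and 0.5, with r = 0 as the worst case.

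**Attained weight.**

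- Unadjusted half-width = t(0.975; 2n − 2) × √(2/n) = 0.0912 SD
- Adjusted half-width = t(0.975; 2n − 3) × √[(2/n)(1 − r²)(1 + 1/(2n − 4))]
- Unadjusted n per arm with the same precision = 924/(1 − r²)

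| r (assumed) | Adjusted half-width (SD) | Change in width | Equivalent extra infants per arm |
|---|---|---|---|
| 0 | 0.0913 | +0.03% | 0 |
| 0.2 | 0.0894 | −2.0% | 39 |
| 0.3 | 0.0871 | −4.6% | 91 |
| 0.4 | 0.0837 | −8.3% | 176 |
| 0.5 | 0.0790 | −13.4% | 308 |

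The percentages are the same at 800 per arm (unadjusted half-width 0.0981 SD) and at 1000 per arm (0.0877 SD).

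**Weight gain as the comparator.** Let k be the SD of baseline weight divided by the SD of later weight. The variance of the gain is proportional to 1 + k² − 2rk, against 1 − r² after adjustment. The two are equal when k = r. For assumed k of 0.4 to 0.7 and r of 0.3 to 0.5, the adjusted interval is between 0% and 7.8% narrower. The maximum is at k = 0.7, r = 0.3: √(0.91/1.07) = 0.922.

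**The same loss seen as chance imbalance** (not an additional one). In 95% of randomisations the arms differ in mean baseline weight by up to 1.96 × √(2/924) = 0.091 SD. Multiplied by r, this moves the unadjusted difference by up to 0.018, 0.027, 0.036 or 0.046 SD at r = 0.2, 0.3, 0.4 or 0.5.

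**Simulation.** In 4000 simulated trials of 924 per arm, both estimates were centred on zero (absolute mean below 0.0006 SD). The ratio of standard errors, adjusted to unadjusted, was 1.00, 0.98, 0.96 and 0.86 at r = 0, 0.2, 0.3 and 0.5. In the tenth of trials with the largest baseline imbalance at r = 0.5 (mean 0.081 SD), the unadjusted estimate was off by 0.042 SD on average and the adjusted one by 0.002 SD.

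**Strata by place of delivery.** Stratum sizes are not given; 100 and 500 per arm are assumed for illustration.

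| n per arm | Unadjusted (SD) | Adjusted, r = 0.2 | Adjusted, r = 0.5 |
|---|---|---|---|
| 100 | 0.279 | 0.274 | 0.242 |
| 500 | 0.124 | 0.122 | 0.107 |

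The relative gain is essentially that of the whole trial. The absolute gain is larger: at r = 0.5 it is 0.037 SD with 100 per arm, against 0.012 SD with 924.

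**The case against.** The strongest reply is that this is a preference for efficiency and not an error. An unadjusted comparison in a randomised trial of 2000 infants is valid. Growth is one of several secondary outcomes, is reported without a p-value, and is not among the outcomes SAP 30 lists for the main paper. All of this stands, and it limits the weight of the point.

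A second reply is that the t-test sentence does not name growth either, so SAP 18 could equally govern growth, and repeated measurements make growth a natural candidate for the mixed models in SAP 29. This stands in part: the plan does not commit growth to a t-test. But a general promise of regression and a package name do not identify a model, and no covariate is named for any between-arm comparison. On either reading baseline adjustment is not prespecified.

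A third reply concerns size. The upper figures need r = 0.5, and a gain score leaves less to win. The visit windows in the protocol summary (35–50 and 170–190 days) add age-related spread to raw weight, which would tend to lower r. These are fair cautions. They argue for the lower part of the range, not for leaving the covariate out, since the worst-case penalty is 0.03%.

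Fourth, the covariate for length is uncertain. Protocol 3.8.5 mentions only weighing at enrolment and gives length for the study visits. Protocol 3.8.2 counts three visit CRFs and Table 1 assigns the first to enrolment, so enrolment length may or may not be recorded. The figures above are for weight; for length or z-scores the same formula applies, with r between the covariate used and that outcome.

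Finally, the plan does not fix the scale of growth (attained size, gain or z-score). That is true, and the new text should settle it.

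**Conclusion.** The point holds. The only method the documents state for comparing means is unadjusted, and the regression and mixed models named elsewhere are tied neither to growth nor to a covariate. Adjustment is not excluded, but it is not prespecified.

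The consequence is modest: a wider interval than necessary on a secondary outcome, with no bias and no claimed change of conclusion. For attained weight the avoidable width is 2% to 13% under assumed r of 0.2 to 0.5. Against a gain score it is 0% to 8% under assumed r of 0.3 to 0.5 and SD ratio of 0.4 to 0.7. Both ranges rest on values the documents do not give. The change should be made because it costs almost nothing and removes a choice that would otherwise be made after the data are seen.

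**What to change.** In SAP 27, add that the arm difference in weight and in length, at six weeks and at six months, will be estimated by linear regression at each visit with arm and baseline weight as terms. Then settle the following:

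- **Scale.** Choose measured values or z-scores, and say which.
- **Baseline.** State whether it is birth weight or enrolment weight. The two may differ, since home deliveries can be enrolled up to day 3. For length, use enrolment length if the CRF records it, otherwise baseline weight.
- **Alternative model.** A single mixed model with lme4 would also serve. It then needs visit and arm-by-visit terms so that each visit has its own difference.
- **Reporting.** Give the adjusted mean difference with its 95% CI, and keep the unadjusted difference as a check.
- **Strata.** Use the same model within the place-of-delivery strata.
- **Cross-references.** Point SAP 18 and SAP 29 to this model.

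The cost is two or three SAP sentences, fixed before unblinding. No new data, visits or infants are needed.
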